across 3 racial/ethnic groups (White, Black, Hispanic). These differences will be examined in bivariate analyses (unadjusted) and multivariable analysis (adjusted). We will develop multilevel multivariable regression models to examine the association between predictors, mediators, and moderators on the primary outcome (testing uptake) and secondary outcomes (COVID mitigation practices, and family mutual aid). We will use multivariable multilevel logistic (binary outcomes) and linear (continuous outcomes) regression models to conduct cross-sectional analysis at each time point. For outcomes where statistical distributional assumptions are violated we will use the *non-parametric multilevel mixture model (NPMM)*. In this model, latent classes are extracted at multiple levels of a hierarchical data structure (e.g., individual, household) and, unlike the conventional multilevel models (MLM), there are no continuously distributed random effects.^{1,2}

Longitudinal Analysis

We will use a random-intercepts logistic (with a binary response) or linear (continuous outcome) multilevel regression model, for each timepoint t , individual i , that is a member of household j . A random-intercepts model will give the conditional assessment of the extent to which household-level exposures vary on the outcomes after taking into account individual-level exposures, assuming the household-level variation is normally and independently distributed with a constant variance. The variance partitioning coefficient (VPC), or the amount of variability in the outcome attributed to predictors at each level, will be calculated. This will tell us to which extent household level and individual-level variables contribute to the outcome allowing for an examination of the impacts of COVID-19 at multiple levels. Structural equation models (SEM) will be used to examine mediating and moderating variables in the regression analyses. In addition, we will conduct sensitivity analyses (e.g., intent to treat vs receive intervention, components of intervention received, per protocol) and subgroup analyses (e.g., race/ethnicity, gender, age, education, essential worker) based on findings from aims 1-3.

For binary outcomes, we will use a random-intercepts logistic multilevel regression model, for each timepoint t , individual i , that is a member of household j . The basic equation will follow the form:

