$$y_{tij} = \ln\left(\frac{\pi_{tij}}{1 - \pi_{tij}}\right) = B_0x_{0ij} + \beta_1x_{tij} + \beta_2x_{ij} + \beta_3x_j + \varepsilon_{i(j)}^{(2)} + \varepsilon_j^{(3)}$$

For continuous outcomes, we will use a random-intercepts multilevel regression model, for each timepoint t , individual i , that is a member of household j . The basic equation will follow the form:

$$y_{tij} = B_0x_{0ij} + \beta_1x_{tij} + \beta_2x_{ij} + \beta_3x_j + \varepsilon_{i(j)}^{(2)} + \varepsilon_j^{(3)}$$

A random-intercepts model will give the conditional assessment of the extent to which household-level exposures vary on the outcomes after taking into account individual-level exposures, assuming the household-level variation is normally and independently distributed with a constant variance. Where y_{tij} represents the outcome for the i^{th} individual that resides in household j and time t , x_{tij} denotes the vector of time-varying covariates (e.g., exposure to COVID-19, household member exposed, household member infected), x_{ik} denotes the vector of individual-level variables (e.g., age, gender, race, ethnicity, comorbidities), and x_k is a vector of household-level variables (e.g., household plan developed). The vector of regression coefficients for the time-varying variables is denoted as β_1 ; similarly, β_2 denotes the vector of regression coefficients for the individual-level variables, and β_3 denotes the vector of regression coefficients for the household-level variables.

The random effect for individual i that is a member of household j is denoted by $\varepsilon_{i(j)}^{(2)}$, and $\varepsilon_j^{(3)}$ denotes the random effect for the third (household-level) cluster. We assume the random effects are independent and normally distributed [5-7]. The variance partitioning coefficient (VPC), or the amount of variability in the outcome attributed to predictors at each level, will be calculated. This will tell us to which extent household level and individual-level variables contribute to the outcome allowing for an examination of the impacts of COVID-19 at multiple levels. In order to examine these impacts, a test for the difference in two proportions using a mixed-effects regression model based on a clustered 3-Level Hierarchical Design with level-3 (household) randomization will be utilized.

Mediation, moderation, and mediated moderation, moderated mediation analyses

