Consensus has yet to be determined on the precise power calculations for multilevel models[1-3]. Subramanian and other respected scholars in multilevel modeling argue that if the purpose of the multilevel model is to estimate the variation of level-1 variables, the size of the level-1 variable is really the driving factor [2,3]. Power for the proposed study was calculated using Power Analysis and Sample Size software (PASS 2020) based on household level randomization, individual level outcomes using conservative estimates and adjusting for 15% attrition and allowing for subgroup analyses [4]. A test for the difference in two proportions using a mixed model based on a clustered 3-Level Hierarchical Design with level-3 (household) 2:1 intervention: control randomization. The total sample size of 300, obtained from 100 level-3 units (households) in the intervention group and 50 level-3 units in the control group with an average of 2 level-2 units (individuals) per level-3 unit (household) and an average of 3 level-1 units (timepoints) per level-2 unit (individual), achieves >80% power to detect a difference between the group proportions of at least 0.15. The proportion in group 2 is 0.10. The correlation of level-1 units within a level-2 unit is <0.7. The correlation of level-2 units within a level-3 unit is <0.3. A test based on a mixed-effects logistic regression is anticipated at a significance level of 0.05.

References:

2. Snijders AT. Power and sample size in multilevel modeling. 2005;3:1570-1573.
3. NCSS LLC. PASS 2020 Power Analysis and Sample Size Software; 2020. ncss.com/software/pass.
6. Robinson TJ. Multilevel Analysis: Techniques and Applications. *J Am Stat Assoc*. 2003;98(462):496-496.
7. Hox JJ. Multilevel Analysis: Techniques and Applications. Psychology Press; 2002.
8. Joreskog, K. G., & Sorbom D. (1988). PRELIS: A Program for Multivariate Data Screening and Data Summarization. A Preprocessor for LISREL. Chicago: SSI, Inc.
9. Joreskog, K. G. (1978). Structural analysis of covariance and correlation matrices. *Psychometrika*, 43, 443-477.

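### The SAP reads the variance partitioning coefficient as variability due to predictors; in adjusted models it is a share of residual variance, so it cannot show how far household and individual variables contribute

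*SAP*

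**What the plan says.** The definition appears twice in the SAP's Longitudinal Analysis section, once before and once after the model equations. Both times the VPC is glossed with the words "or the amount of variability in the outcome attributed to predictors at each level". The use to be made of it follows directly: "This will tell us to which extent household level and individual-level variables contribute to the outcome".

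The models from which the VPC would come contain covariates at three levels: time-varying, individual and household. No model without covariates is mentioned, and no step compares variance components between models.

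Two equations are given. The logistic one, for binary outcomes, has fixed effects plus an individual and a household random effect. The second is introduced with "For continuous outcomes, we will use a random-intercepts multilevel regression model" and has exactly the same right-hand side. The text beneath defines two random terms only: "The random effect for individual i that is a member of household j is denoted by" one symbol, and the other "denotes the random effect for the third (household-level) cluster". Neither the second equation nor the text has a residual that varies from one time point to the next. For the logistic model, the SAP does not say what level-1 variance, or what scale, its VPC will use.

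**The concern.** A VPC divides the variance left over after the fixed effects among household, individual and time point. It describes clustering that the predictors have not accounted for. The SAP assigns it a different job, that of measuring what the predictors account for. Someone who computes the coefficient correctly and then reports it as the SAP directs would make a statement that the number does not support.

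Households are randomized and receive the intervention as units (Protocol, Trial design {8}), and the household-level vector includes whether a household plan was developed. Readers will therefore care how much household factors contribute, and the SAP offers the VPC as the answer.

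The missing residual is a separate matter of notation. A linear model for repeated measures needs a level-1 error term. Without one, two measurements on the same person with the same covariates would have to be equal, and a VPC from the model would give no share to variation over time.

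**Working it through.** **Inputs.** The documents give no VPC and no variance components. The nearest figures are the planning correlations in SAP, Power and Sample Size, stated for the binary outcome: below 0.7 between time points within a person and below 0.3 between members of a household. The same section gives "100 level-3 units (households) in the intervention group and 50 level-3 units in the control group", 2 people per household, 3 time points per person, a control proportion of 0.10, a difference of 0.15 and significance level 0.05. SAP, Final Analysis makes tests two-sided.

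**1. The plan's own figure.** With M = 3 time points and K = 2 people, the design effect is 1 + (M − 1)(0.7) + M(K − 1)(0.3) = 1 + 1.4 + 0.9 = 3.3. Effective observations are 100 × 6 / 3.3 = 181.8 and 50 × 6 / 3.3 = 90.9. Power for 0.25 versus 0.10 is 0.864 (pooled null variance) or 0.916 (unpooled), in line with the stated figure of more than 80%. With 15% fewer households it is 0.798 or 0.868. No VPC enters this calculation.

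**2. Illustrative variance shares (assumption).** Set total residual variance to 1 and use the correlation bounds as shares: household 0.3, individual 0.7 − 0.3 = 0.4, time point 1 − 0.7 = 0.3. The VPC at a level is that level's variance divided by the sum of all three, so the shares are 0.30, 0.40 and 0.30.

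**3. A household predictor that absorbs existing household variance.** If it accounts for half, household variance falls from 0.30 to 0.15. The adjusted household VPC is 0.15 / (0.15 + 0.40 + 0.30) = 0.15 / 0.85 = 0.176. The predictor explains 0.15 of the total variance, and the VPC has gone down.

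**4. A household predictor whose variance is additional.** Simulation of 60,000 households of 2 people and 3 time points, with a binary household predictor present in two thirds of households (variance 2/3 × 1/3 = 2/9):

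| Coefficient | Variance added | Predictor's share of total | Household VPC, adjusted | Household VPC, null |
|---|---|---|---|---|
| 0 | 0 | 0 | 0.300 | 0.300 |
| 0.5 | 0.056 | 0.053 | 0.298 | 0.334 |
| 1 | 0.222 | 0.182 | 0.300 | 0.424 |
| 2 | 0.889 | 0.471 | 0.297 | 0.627 |

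The adjusted VPC does not move while the predictor's share rises to 0.47. The comparison of models does recover the contribution. At coefficient 1 the household variance is 0.3 + 0.222 = 0.522 in the null model and 0.3 in the adjusted one; the fall of 0.222, over a total of 1.222, is 0.182.

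**5. The printed continuous equation, taken literally.** Without the time-point variance the household share is 0.3 / 0.7 = 0.43 and the individual share 0.4 / 0.7 = 0.57. Both are multiplied by 1 / 0.7 = 1.43, and the ratio stays 3:4. With lower assumed correlations of 0.5 and 0.2, the household share goes from 0.20 to 0.40. With 0.3 and 0.1, it goes from 0.10 to 0.33.

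**6. Logistic model.** On the latent scale, level-1 variance is π²/3 = 3.29. Correlations of 0.7 and 0.3 then imply a total of 3.29 / 0.3 = 10.97, with household 3.29 and individual 4.39, so VPCs of 0.30 and 0.40. Leaving out the 3.29 gives 0.43 and 0.57, which is why the SAP needs to say what it uses.

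**The case against.** The best defence is that these are wording and notation matters in a descriptive add-on. Much of that stands.

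- The equations are offered as basic forms. The second repeats the first, for which no additive residual is needed, and the covariate subscripts in the equations differ from those in the text. Standard linear mixed-model routines, such as those in the packages the SAP names, estimate a residual variance by default. The omission is probably a slip that would never reach a fitted model.
- Predictor effects are already to be estimated as regression coefficients. The treatment comparison is a separate test of two proportions in a mixed-effects model.
- Null-versus-adjusted comparison is one convention among several for describing contribution, and π²/3 is one choice of level-1 scale.

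Two stronger readings are tempting. A reader might infer that household variables will look less important precisely when they explain more. The documents do not support that as a general rule: it needs models with and without the predictor to be compared while household variance is otherwise fixed, the SAP plans no such comparison, and step 4 shows a flat VPC. A reader might also infer that the missing residual falsifies the household-versus-individual comparison. It does not, because both shares are inflated by the same factor.

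The defence does not reach the definition. It is stated twice, with the inference spelled out, and no choice of software corrects it.

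**Conclusion.** Wrong as written, minor. The VPC from the planned adjusted models is a share of residual random-effect variance. It may fall or stay flat as a household predictor explains more, so the SAP's conclusion about how far household and individual variables contribute does not follow from it. The missing level-1 residual is a probable notation slip that should be corrected along with it.

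The sizes (0.30 to 0.18, flat at about 0.30, and 0.30 to 0.43 if the equation were followed literally) rest on using the planning correlation bounds as variance shares. They show the kind of effect and do not predict this trial's results.

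A reader might go further and infer that the efficacy result is in doubt. It is not. The primary outcome is binary and uses the logistic equation, where no additive residual belongs, and neither the treatment test nor the power calculation uses the VPC.

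**What to change.** In SAP, Longitudinal Analysis:

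- Define the VPC, in both places, as the share of random-effect variance at each level given the covariates in the model, and remove the statement that it shows the contribution of variables.
- State the level-1 variance for logistic models, for example π²/3 on the latent scale.
- Describe predictor contributions by the fixed effects, or by the change in each variance component between a null and an adjusted model. In logistic models the level-1 variance is fixed, so adding time-varying predictors rescales the other components; the fixed effects are easier to interpret there.
- Add a level-1 residual e_tij, with its variance, to the continuous-outcome equation and to the list of random terms.

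The cost is SAP wording and, if the variance-change route is taken, one null model per outcome. No data collection, sample size or primary analysis changes.

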## **Abstract**

*Background:* The impact of COVID-19 has been unequal across the nation in regards to number of cases, hospitalizations and deaths. Notably, primary strategies employed for COVID-19 mitigation at the national, state, and local levels (i.e. COVID-19 testing, vaccination rollouts, etc) often have inadequate reach in communities that experience COVID-19 disparities. Therefore, new approaches for COVID-19 mitigation are needed to more effectively reduce disparities. The current trial tests a novel approach by evaluating the efficacy of the Nurse-Community-Family Partnership (NCFP) intervention to improve primary (COVID-19 testing uptake) and secondary (COVID-19 vaccine uptake, adoption of COVID-19 infection control measures, household mutual aid capacity, and seasonal influenza vaccine uptake) outcomes in a community experiencing disproportionate COVID-19 morbidity, mortality, and barriers to mitigation.

*Methods:* In this two-arm parallel randomized control trial, we will evaluate the efficacy of the NCFP intervention in improving the primary and secondary outcomes. We will recruit 150 households from the Bronx in New York City. These households will be randomized in a 2:1 ratio, intervention:control, using a computer-generated algorithm. The NCFP intervention will take place over 5 months. The core components of the intervention include regular home visits by nurses and community health workers, development of a household-specific infection control plan, offer of at-home COVID-19 tests, and navigation to COVID-19 vaccination and other ancillary services. NCFP intervention components and intensity is informed by a household risk algorithm (low, medium, high). All households will complete a baseline assessment, monthly follow-up surveys during months 1-6 post baseline, and a delayed 9-month follow-up survey. We will use intent-to-treat analysis to evaluate the efficacy of the intervention in improving the primary and secondary outcomes compared to the standard of services. Subgroup analyses based on select household characteristics will be conducted.

*Discussion:* The NCFP intervention may have utility for mitigating COVID-19 at the household level—a novel and promising approach. If the trial achieves this, this care delivery model relying on a partnership between nurses, community health workers, and families will expand the available cadre of effective strategies for COVID-19 mitigation in underserved communities.

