Analyses for Aim 1 will include a descriptive examination of household COVID testing uptake and previous COVID testing utilizing the COVID-19 Symptoms, Diagnoses, and Testing Scale for participants at baseline. This scale includes variables such as symptoms, whether participant has ever been tested for COVID, and COVID test results. These data are dichotomous and nominal in nature. To address Aim 1, the following analyses will be conducted. Data will be stratified with respect to important demographic factors (e.g., age, race, gender, ethnicity, essential worker). Nominal variables (i.e. COVID-19 symptoms, test frequency) will be summarized using frequencies and percentages. Bivariate analyses will be conducted to examine associations between testing practices and key predictors (intervention group), confounders (i.e. previous infection or vaccination), moderators (i.e. essential worker status, testing fatigue), and demographic characteristics (e.g., age, gender, race, ethnicity). A two-sample test for proportions will be used to compare the baseline testing practices of the two treatment groups. Chi-square tests will be used to assess group differences for nominal data. The Fisher's exact test will be considered for contingency tables with sparse cells. We will compare outcomes across 3 racial/ethnic groups (White, Black, Hispanic). These differences will be examined in bivariate analyses (unadjusted) and multivariable analysis (adjusted). We will develop multilevel multivariable regression models to examine the association between the key predictors, mediators, and moderators, such as vaccination, testing fatigue, or exposure, on baseline testing uptake.

Aim 2 is to explore acceptability, facilitators and barriers to testing, social distancing, wearing face masks, naming contacts, isolation or quarantine, and accessing COVID-19 related health services.

Analysis for Aim 2

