Analyses for Aim 2 will include an analysis of variables collected utilizing tools adapted from the following validated scales: Avoidant Behaviors Scale (CESR, 2020), Contact Tracing Cooperation Scale, COVID-19 Household Environment Scale (Behar-Zusman, 2020), COVID-19 Family Impact Survey (The Center for Pediatric Traumatic Stress, 2020), COVID-19 Parent Relationships Scale (UCSD, 2020), and their relationships with key predictors (COVID-19 exposure), confounders (i.e. previous infection or vaccination) and moderators (i.e. age, gender, essential worker status). These scales capture variables such as reasons why participant was not tested, attitudes toward people who get tested, and workplace PPE accessibility. Variables included in the analysis for Aim 2 are nominal, ordinal, and discrete in nature. The initial analysis will summarize the variables of interest at the individual and household level for the baseline and follow-up timepoints. Nominal and ordinal variables will be summarized using frequencies and percentages. Bivariate analyses will be conducted to examine associations between the facilitators and barriers to COVID-19 precautions and key predictors (intervention group), confounders (e.g., previous infection, vaccination, moderators (e.g. gender, testing fatigue), and demographic characteristics (e.g., age, race, essential worker). To examine bivariate associations between continuous variables that are approximately normal or may become approximately normal after an appropriate transformation, the Student's t-test will be used. For other continuous variables where normality cannot be assumed, the Wilcoxon rank-sum test will be used instead. Chi-square tests will be used to assess group differences for nominal data. We will use Chi-square tests and the Cochran Mantel-Haenszel tests for comparison in ordinal characteristics (i.e. how often participant washes hands, uses PPE, agreeableness to isolate). The Fisher's exact test will be considered for contingency tables with sparse cells. We will compare outcomes across 3 racial/ethnic groups (White, Black, Hispanic). These differences will be examined in bivariate analyses (unadjusted) and multivariable analysis (adjusted). We will develop multilevel multivariable regression models to examine the association between predictors, mediators,

and moderators on COVID protection practices.

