The analysis for Aim 3 will encompass the variables collected regarding modes of transportation, access to healthcare, drug and alcohol cessation treatment, and street drugs. Descriptive analyses will include participant and household level use of public health mitigation strategies at each of the time points for the randomized controlled trial. Data will be stratified with respect to important demographic factors (e.g., age, race, gender, ethnicity). Continuous variables will be summarized using the mean, standard deviation, median, range, and interquartile range, while nominal and ordinal variables will be summarized using frequencies and percentages. Each scale will be scored according to established guidelines. Each of the items in each scaled will be examined individually in addition to the composite score variable. Chi-square tests will be used to assess group differences for nominal data (e.g. reasons for not obtaining medication for chronic conditions). We will use Chi-square tests and the Cochran Mantel-Haenszel tests for comparison in ordinal characteristics (e.g., agreeability to use public transportation). The Fisher's exact test will be considered for contingency tables with sparse cells. We will compare outcomes across 3 racial/ethnic groups (White, Black, Hispanic). These differences will be examined in bivariate analyses (unadjusted) and multivariable analysis (adjusted). We will develop multilevel multivariable regression models to examine the association between predictors (COVID-19 exposure), mediators (e.g., self-efficacy, medical mistrust), and moderators (e.g., household COVID cases, participant age), on COVID mitigation practices. We will use multivariable multilevel logistic (binary outcomes) and linear (continuous outcomes) regression models to conduct cross-sectional analysis at each time point. For outcomes where statistical distributional assumptions are violated we will use the *non-parametric multilevel mixture model (NPMM)*. In this model, latent classes are extracted at multiple levels of a hierarchical data structure (e.g., individual, household) and, unlike the conventional multilevel models (MLM), there are no continuously distributed random effects.^{1,2}

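### The SAP lets findings from Aims 1–3 choose the efficacy subgroups, and through Aim 2 that choice can rest on by-arm follow-up data from the same participants

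*SAP*

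**What the plan says.** The SAP's Longitudinal Analysis section, under Aim 4, plans "subgroup analyses (e.g., race/ethnicity, gender, age, education, essential worker) based on findings from aims 1-3". It does not say which findings trigger a subgroup, gives no cut-points, and does not call the results exploratory. The Final Analysis section declines any multiplicity adjustment on the ground that the primary outcome is clearly defined.

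The three aims that feed the choice differ:

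- **Aim 1** compares the arms at baseline only: "A two-sample test for proportions will be used to compare the baseline testing practices of the two treatment groups".
- **Aim 2** summarises "variables of interest at the individual and household level for the baseline and follow-up timepoints", and its bivariate analyses examine "associations between the facilitators and barriers to COVID-19 precautions and key predictors (intervention group". It goes on to multilevel models with moderators.
- **Aim 3** describes "participant and household level use of public health mitigation strategies at each of the time points for the randomized controlled trial", but its models "examine the association between predictors (COVID-19 exposure", with arm not named.

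Aim 4, the efficacy analysis, reuses the variables of all three aims.

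Four places list candidate factors, and they do not agree:

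- **Protocol, Abstract:** "Subgroup analyses based on select household characteristics will be conducted", with none named.
- **Protocol, Statistical methods {20a}:** essential worker status and testing fatigue, as moderators.
- **SAP, Moderating Variables:** gender, race/ethnicity, age and testing fatigue.
- **SAP, Longitudinal Analysis:** race/ethnicity, gender, age, education and essential worker status.

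**The concern.** A subgroup test keeps its nominal error rate only if the factor was chosen without sight of how the arm difference varies across it. Here the plan makes the choice depend on analyses of the same randomised participants, and at least one of those analyses can use arm and post-randomisation data.

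Two Aim 2 instruments are also trial outcomes. The avoidant-behaviours questionnaire is the source of control-measure uptake, and the COVID-19 Household Environment Scale measures family mutual aid. For those secondary outcomes the selecting data and the testing data can be identical. The Interim Analyses section also has cross-sectional analyses completed after each time point, so six-month Aim 2 results could be known before the nine-month analysis is set up.

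What is at stake is the credibility of any reported subgroup effect. If only the subgroups that looked promising are tested and reported, a reader cannot know how many were considered or what the reported p-value means.

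**Working it through.** **1. The plan's own figure.** No subgroup error rate or subgroup power is stated. The nearest figure is the overall power above 80% in Power and Sample Size, which is said to allow for subgroup analyses. Inputs from that section are 100 and 50 households, K = 2 individuals, M = 3 time points, proportions 0.25 and 0.10, and correlations taken at their upper bounds of 0.7 and 0.3.

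- Design effect: 1 + (M − 1)(0.7) + M(K − 1)(0.3) = 1 + 1.4 + 0.9 = 3.3.
- Effective numbers: 100 × 6 / 3.3 = 181.8 and 50 × 6 / 3.3 = 90.9.
- Two-sided power at 0.05: 86.4% (pooled variance) or 91.6% (unpooled). After 15% attrition it is 79.8% or 86.8%.

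The overall figure therefore reproduces before attrition, and sits at or above roughly 80% after it.

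**2. What that leaves for an interaction.** Assume a household-level factor that splits the sample in half, with a difference of 0.15 in one half and 0 in the other.

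- Effective numbers per half: 90.9 (intervention) and 45.45 (control).
- Variance: 0.09/45.45 + 0.1875/90.9 + 0.09/45.45 + 0.09/90.9 = 0.00701, so SE = 0.0837.
- Power: Φ(0.15/0.0837 − 1.96) = about 43%, or 38% after 15% attrition.

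True interactions would often be missed, so false ones would make up a larger share of those found.

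**3. Error from selecting, then testing.** Take k null factors with independent interaction statistics. Pick the factor with the largest absolute interaction statistic on a screening outcome. Then test that factor at two-sided 0.05 on an outcome whose interaction statistic has correlation r with the first. At r = 1 the result is exact, 1 − 0.95^k. The other rows come from a null simulation with 400,000 replicates.

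| r | k = 5 | k = 6 | k = 10 |
|---|---|---|---|
| 0 | 5.0% | 5.0% | 5.0% |
| 0.3 | 6.8% | 7.0% | 7.9% |
| 0.5 | 10.0% | 10.7% | 13.1% |
| 0.7 | 14.5% | 16.1% | 21.0% |
| 0.9 | 19.9% | 22.9% | 32.6% |
| 1 | 22.6% | 26.5% | 40.1% |

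The documents give neither k nor r. Five is the number of factors in the SAP's list, six adds testing fatigue, and ten illustrates what an open list could become. The r = 1 row corresponds to an outcome that serves for both selection and testing, as could happen with the two shared Aim 2 instruments at the same time point. The primary outcome, testing at nine months, is analysed by arm under Aim 4, so Aim 2 can influence it only at whatever lower r applies.

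**4. Error from testing the whole list.** Five fixed factors tested unadjusted give 1 − 0.95^5 = 22.6%, and six give 1 − 0.95^6 = 26.5%, assuming independence. This is a separate quantity from selection error, and closing the list does not reduce it.

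**The case against.** The strongest reply is that by-arm selection is inferred. Aims 1–3 specify no arm-by-factor test. In Aim 2, arm, confounders, moderators and demographics appear as separate bivariate associations, and the by-arm tests carry no stated time point. The explicit mention of follow-up belongs to the descriptive summary. Choosing age because uptake differs by age overall would not materially inflate a later arm-by-age test. That last point is right, and it is roughly the r = 0 row.

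It does not dispose of the matter. The Statistical Methods section plans analysis at each time point, Aim 2 goes on to model moderators, and the SAP's Moderating Variables section defines these as modifying the intervention's association with the outcomes. Selection on arm-by-factor patterns is a fair reading of the plan, and nothing in it rules that out.

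Four stronger readings are tempting, but the documents do not support them:

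- *All three aims reveal treatment effects by arm.* Aim 1 is baseline only, and Aim 3 names exposure as the predictor.
- *Every subgroup is invented after the fact.* Four of the five listed factors are named elsewhere as moderators: gender, race/ethnicity and age in Moderating Variables, and essential worker status in Protocol {20a} and in Aims 1 and 2. Only education is not. A moderation method, multiple-group SEM, is also given.
- *The 22.6% measures the damage done by selection.* It is the upper end for five candidates, and equals the rate for testing all five without any selection.
- *The protocol restricts subgroups to household characteristics and the SAP contradicts it.* The abstract wording is loose, and the protocol's own methods section names individual-level moderators.

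**Conclusion.** The point holds in limited form. The SAP states a results-driven rule for choosing efficacy subgroups from an open list, Aim 2 gives that rule a plausible route to by-arm follow-up data, and no section labels subgroups exploratory or controls their error.

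With five candidates, the actual error of a nominal 5% test lies between 5% and 22.6%. Where it falls depends on an assumed correlation, on independence between factors, and on selection having used arm-by-factor patterns. It would be highest for control-measure uptake and family mutual aid, and lower for testing uptake. A reader might infer that subgroup p-values become meaningless or that the main result is compromised. Neither follows: the inflation is bounded under stated assumptions, and the overall comparison of arms does not depend on which subgroups are chosen. This is a low-severity point that is cheap to correct.

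**What to change.** - In the SAP's Longitudinal Analysis section, delete the clause that ties subgroup choice to the results of Aims 1–3.
- State one closed list of subgroup factors, defined at baseline, with categories or cut-points for age and education. It should reconcile the Protocol Abstract, Protocol {20a}, SAP Moderating Variables and SAP Longitudinal Analysis.
- Decide explicitly on testing fatigue, which both documents name as a moderator but the Longitudinal Analysis list omits, and on education, which is in that list but not named as a moderator. The SAP does not say when testing fatigue is measured. Only a pre-randomisation value would do, because the intervention itself offers repeated testing.
- Test each factor with one joint arm-by-factor interaction test in the multilevel model. For race/ethnicity in three groups this has 2 degrees of freedom.
- Report every listed factor as exploratory, whatever the result, and label any subgroup suggested by Aims 1–3 as post hoc.
- State that the SEM moderation analysis uses the same list.

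The change removes selective choice. It does not lower the chance of at least one false positive across the list (about 23% for five independent tests, 26.5% for six), so the exploratory label has to carry that.

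The cost is aligned wording in several sections of both documents, and a post hoc label on later subgroup ideas. No data collection or sample size changes.
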